# 4 Study Design

### 4.1 Primary Study Endpoints/Secondary Endpoints

When examining the baseline microbiome as a whole, characterizing the distribution of 16S bacterial sequences present is the 'endpoint'. The study will also look at changes to the baseline microbiome following decolonization regimens.

### 4.2 Study Design/Type

This is a single-center, interventional study to describe the microbiome sequentially over a 16 week period in *S. aureus* colonized adults, both before and after administration of topical antiseptic agent (CHLORHEXIDINE) and intranasal antimicrobial ointment (MUPIROCIN). Eighty male and female community dwelling participants residing in the Baltimore area will be recruited and screened to document their health status, with the goal of 50 participants completing the study.

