# **Protocol Summary**

**Title**: Metagenomic Studies of MRSA Colonization - Nose, Throat, and Skin Cultures before and after use of Antibacterial Nasal Ointment and Antibacterial Soap for Showering in Adults who live in the Community and have Current *S. aureus* Colonization

**Population**: Approximately 250 male and female adults with *S. aureus* colonization at enrollment from a single geographic location in the US to achieve a final sample size of at least 40.

Site: Baltimore VA Medical Center

[figure not shown]
Study Duration: Approximately 18 months

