### 5.2 Inclusion Criteria

- Adults living independently in the Baltimore area
- Willing and able to provide anterior nares, throat, skin, and perirectal specimens over up to an 18 week time period.
- Willing and able to administer intranasal mupirocin and topical chlorhexidine over a five day period.
- Capable of understanding and complying with the entire study protocol.
- Provided signed and dated informed consent.
- *S. aureus* colonization on at least one of the enrollment cultures (after informed consent)

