#### 11.3 Sample Size Estimates

How many participants (or specimens, or charts) will be used in this study? Local: 250 Worldwide: 250

We plan on enrolling 250 participants to end up with a final sample size of 40. We assume that approximately one in five participants will have *S. aureus* colonization at the screening/enrollment visit. We assume that 10 participants will become ineligible during the course of the protocol because of hospitalization or antibiotic administration. The final sample

size was chosen based on feasibility and cost. Unlike more traditional genetic association studies, where theoretical sample calculations can be performed, the current study uses more novel data mining approaches applied to data obtained from high-throughput genotyping technology, in which many different potential OTUs are compared between groups (pre and post decolonization within a participant). Currently, there is no generally accepted theoretical power calculations for the analyses proposed here. Since the participants will serve as their own controls (pre and post decolonization), we increase power to detect significant differences and potentially avoiding confounding factors (27).

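### Section 4.2 plans 80 screened and 50 completing, which conflicts with the 250 enrolled and 40 final in Section 11.3 and cannot be met at the protocol's own colonization rate

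*Protocol*

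**What the plan says.** The protocol gives its recruitment and final numbers in three places.

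- **Section 4.2 (Study Design/Type):** "Eighty male and female community dwelling participants residing in the Baltimore area will be recruited and screened", "with the goal of 50 participants completing the study".
- **Section 11.3 (Sample Size Estimates):** "We plan on enrolling 250 participants to end up with a final sample size of 40". Two assumptions support this: "We assume that approximately one in five participants will have" *S. aureus* colonization at the screening/enrollment visit, and "We assume that 10 participants will become ineligible during the course of the protocol because of hospitalization or antibiotic administration". The section adds that the final size was chosen on feasibility and cost.
- **Protocol Summary (Population):** "Approximately 250 male and female adults with *S. aureus* colonization at enrollment", to reach a final sample of at least 40.

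The eligibility rules connect these numbers. Section 5.2 requires "colonization on at least one of the enrollment cultures (after informed consent"), and Section 5.4 withdraws anyone whose visit 1 specimens are all negative. Colonization status is therefore learned after a person has consented and been sampled.

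**The concern.** Section 4.2 and Section 11.3 describe different studies in size. One starts with 80 people and ends with 50; the other starts with 250 and ends with 40. The smaller intake is paired with the larger yield. Since only culture-positive people continue, that pairing can hold only if most of those screened are colonized, while Section 11.3 expects about one in five.

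The numbers matter in practice. They set how many adults are consented, sampled at five body sites and bled 40 mL at Day 0 (Section 8.1), and how many remain for the before/after microbiome analysis and the community versus nursing home comparisons in Sections 11.1 and 11.2. Section 2.4 commits the study to the approved protocol, and it cannot comply with both figures.

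The Summary adds an ambiguity about whether its 250 are people screened or people already known to be colonized.

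**Working it through.** **Inputs**

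| Quantity | Value | Source |
|---|---|---|
| Recruited and screened | 80 | Section 4.2 |
| Goal for completion | 50 | Section 4.2 |
| Enrolled | 250 | Section 11.3 |
| Colonized at screening/enrollment | about 0.20 | Section 11.3 |
| Later ineligible | 10 | Section 11.3 |
| Final sample | 40 | Section 11.3 |

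**Step 1. Reproduce the plan's own figure.** Final number = enrolled x colonization rate - losses.

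250 x 0.20 = 50 colonized; 50 - 10 = 40. Section 11.3 reproduces exactly.

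**Step 2. Apply the same formula to Section 4.2.** 80 x 0.20 = 16 colonized before any loss. The protocol gives losses only as a count of 10, so three versions are shown:

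- no loss: 16 completers;
- fixed loss of 10: 16 - 10 = 6;
- loss in the same proportion (10/50 = 20%, an assumption, since the protocol states no rate): 16 x 0.80 = 12.8, about 13.

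All are far below 50.

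**Step 3. Colonization rate needed for 50 completers from 80.**

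- no loss: 50/80 = 62.5%;
- 10 lost: 60/80 = 75%;
- 20% lost: (50/0.80)/80 = 62.5/80 = 78%.

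Even the lowest of these is more than three times the stated rate.

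**Step 4. Allow for chance and for a higher rate.** Exact binomial probability of at least 50 colonized among 80, before any loss:

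| Assumed rate | Expected colonized | P(at least 50) |
|---|---|---|
| 0.20 (Section 11.3) | 16 | 1.4 x 10^-16 |
| 0.40 (illustrative) | 32 | 0.00004 |
| 0.50 (illustrative) | 40 | 0.016 |
| 0.625 (illustrative) | 50 | 0.55 |

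**Step 5. Screening needed for 50 completers at one in five.** 50/0.20 = 250 with no loss; (50 + 10)/0.20 = 300 with 10 lost; 50/0.80/0.20 = 312.5, about 313, with 20% lost.

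**Step 6. The Summary read literally.** If 250 people were already colonized, 250 - 10 = 240 would remain (or 250 x 0.80 = 200), not about 40, and finding them would take 250/0.20 = 1,250 screened. The literal wording therefore does not fit the final sample given in the same sentence. The numbers fit only if the 250 are counted before culture results, as in Section 11.3.

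**The case against.** The best defense is that Section 11.3 is the governing statement. It is the only one with a derivation, it gives 250 both locally and worldwide, and the Summary repeats its 250 and 40. On this view Section 4.2 is one leftover sentence. The 50 in it even equals the number Section 11.3 expects to be colonized before losses, though that link is inference. This explains how the error may have arisen but does not remove it, because Section 4.2 is current text in the design section.

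A second defense is enrichment. Section 5.1 recruits partly from people with a positive *S. aureus* culture in the last three years, and no colonization rate is given for them. But this is one source beside clinic patients, research registries, students and employees, and Section 11.3 gives one in five for participants overall. A rate of 62.5% or more has no support in the document.

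Several stronger readings are tempting, and the document does not support them:

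- **Three incompatible sample sizes.** Numerically there are two plans. The Summary and Section 11.3 agree on 250 and 40; the Summary is only loosely worded about whom the 250 counts. Nor does a goal of 50 by itself contradict a final sample of at least 40.
- **That at least 40 is an error because 40 is only the expected yield.** It reads naturally as a target attached to an approximate intake. A probability of reaching it would depend on treating an approximate rate as exact, and a range for the final number would also need a loss rate that the protocol never states.
- **That precision or power depends on these figures.** The protocol states neither, and rests the size on feasibility and cost.
- **That recruitment would stop at 80.** Section 4.2 contains no stopping rule.

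**Conclusion.** The contradiction between Section 4.2 and Section 11.3 is real, and nothing else in the protocol reconciles it. Under the protocol's own assumptions, 80 screened give about 16 colonized and roughly 6 to 13 completers once losses are counted, against a stated goal of 50. The two intakes differ about threefold (250/80 = 3.1).

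The result rests on the one-in-five rate applying to the 80, which follows from the eligibility rules in Sections 5.2 and 5.4. The upper end of the 6 to 13 range also assumes a proportional 20% loss. Saying that 50 completers cannot be reached is strictly a statement of negligible probability under that rate, not of logical impossibility, but the conclusion also survives a doubling of the rate.

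The Summary problem is smaller: its numbers match Section 11.3, and only its description of the 250 as already colonized is wrong.

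**What to change.** **Section 4.2.** Replace both numbers with those of Section 11.3: about 250 adults consented and cultured, about 50 expected to be colonized, about 40 expected to be evaluable. The sponsor should first confirm that 40 is the intended target. If 50 completers is the real aim, Section 11.3 must change instead, to about 300 screened (10 lost) or about 313 (20% lost) at the stated rate.

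**Protocol Summary.** Reword the population line so that about 250 adults are consented and screened by culture, and those with *S. aureus* colonization (about 50) continue, for a target final sample of about 40. Colonization should stay in that line, because it defines the study population. Giving a range around 40 is optional and not part of this correction.

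**Cost.** Wording in two sections. If 40 is confirmed, there is no design change and no participant beyond those already planned in Section 11.3.

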### 4.3 Duration

Study participants will have a total of 9 cultures of the anterior nares, posterior pharynx, skin over the subclavian vein, skin over the femoral vein and perirectal skin over a period of approximately 52 weeks.

### 5 Selection and Withdrawal of Participants

### 5.1 Recruitment of Study population

All study participants will be adults that live in Baltimore or the surrounding area. Community dwelling participants will be recruited from the Managed Care Clinics of the Baltimore VA Medical Center (via an IRB approved flier), by conducting a screening of the VA medical records for patients with cultures positive for S. aureus in the last three years in the VA Maryland HCS (via an IRB approved letter mailing), and approved VA research registries (via an IRB approved letter). In addition, we will recruit from students and employees of the University of Maryland Baltimore and the VA Maryland HCS (via an IRB approved flier).

When contacted about participation, the study coordinator will review the information from the study flier or letter with the potential participant and answer questions. If the potential subject is interested in participating, the study coordinator will review the eligibility criteria prior to scheduling the Enrollment Visit in the General Clinical Research Center (GCRC) in order to screen out ineligible participants by history. Identifying information will only be collected on those potential participants who are scheduled for the screening/enrollment visit.

### 5.2 Inclusion Criteria

- Adults living independently in the Baltimore area
- Willing and able to provide anterior nares, throat, skin, and perirectal specimens over up to an 18 week time period.
- Willing and able to administer intranasal mupirocin and topical chlorhexidine over a five day period.
- Capable of understanding and complying with the entire study protocol.
- Provided signed and dated informed consent.
- *S. aureus* colonization on at least one of the enrollment cultures (after informed consent)

### 5.3 Exclusion Criteria

- Use of anticancer chemotherapy or radiation therapy (cytotoxic) within the past 6 months
- History of HIV infection with most recent CD4 of <200
- Immunosuppression medications within the past 3 months
- Use of systemic antibacterial or antifungal agents in the past 3 months
- Use of nasal steroids currently or in the past 3 months
- Use of nasal antimicrobial ointment in the past 3 months
- Any current indwelling percutaneous medical device or urinary catheter
- Acute care hospitalization in the past 3 months
- Planned surgery or hospitalization during the study period

- History of an allergic reaction to chlorhexidine or mupirocin
- Oral temperature of >100 F at enrollment visit
- BMI <18 or >35 at enrollment visit

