Chlorhexidine is a broad spectrum antiseptic agent with activity against Gram-positive and negative bacteria as well as fungi. It is available as a topical solution ranging in concentration from 0.5% to 4% without a prescription. Chlorhexidine is used in intensive care units (ICU's) to prevent central line associated blood stream infections (14). Chlorhexidine baths have also been shown to decrease MRSA and VRE acquisition in the ICU setting (15). Chlorhexidine was recently shown to be superior to Povidone-Iodine for surgical site antisepsis (16).

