### 7.2 Dosage, Preparation and Administration of Study Intervention

Participants will be self-treated with antimicrobial antiseptic skin cleanser (4% chlorhexidine) topically 3 times within 5 days before the Week 9 visit. Participants will also be self-treated with BACTROBAN NASAL ointment (mupirocin calcium ointment, 2%) intranasally in the 5 days before the Week 9 visit.

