# 8 Study Procedures/Evaluations

#### 8.1 Clinical Evaluations

Day 0 (enrollment visit) – Will occur in the GCRC:

- Screen participant regarding inclusion and exclusion criteria.
- Obtain informed consent.
- Obtain demographic information and a brief medical history by interview. The brief medical history includes current and recent medications and past medical and surgical history.
- Collect vital signs and basic anthropometric measurements in order to determine eligibility. Participants deemed eligible for the study will be enrolled at this visit.
- Measure oral temperature to screen out participants with febrile infectious disease.
- Complete a brief physical assessment of the culture sites.
- Obtain a 40 mL blood sample and specimens from the following sites: anterior nares, posterior pharynx, skin over the femoral vein, skin over the subclavian vein, and perirectal skin (see SOP for Methods).
- Counsel participant to refrain from using any antibacterial/antiseptic products for 48 hours before visits.
- Counsel participant to refrain from swimming in a chlorinated pool or using a hot tub in the 48 hours before visits.
- Counsel participant to refrain from bathing or showering in the 12 hours prior to the study visit.
- Inform participant that if specimens are negative for *S. aureus*, he/she will be withdrawn from the study at week 4.

For participants who do NOT meet eligibility criteria to continue in the study: (if MRSA and MSSA negative on all enrollment cultures)

- 1) Inform participant via phone that all enrollment specimens were MRSA and MSSA negative and withdraw him/her from the study.
- 2) Complete Participant Deactivation Form

Week 4 – Will occur in the GCRC:

- Review results of cultures from Day 0 to determine eligibility
- Reconfirm participant's willingness to participate in the study.
- Confirm that participant has abstained for the last 48 hours from the following: using any antibacterial/antiseptic products, swimming in a chlorinated pool or using a hot tub.
- Record time and date of last bath or shower.
- Measure oral temperature to screen out participants with febrile infectious disease.
- Collect a focused medical history.
- Review concomitant medications

- Complete a brief physical assessment of their anterior nares, posterior pharynx and skin sites.
- Obtain specimens from the anterior nares, posterior pharynx, skin over subclavian vein, skin over femoral vein and perirectal skin.

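### Prior antiseptic wash is neither an exclusion nor checked at Day 0, so one of the three skin-site baseline sets can reflect recent antiseptic use

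*Protocol*

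**What the plan says.** Section 5.3 sets 3-month look-backs for several exposures that could disturb the baseline flora. These include "Use of nasal antimicrobial ointment in the past 3 months" and "Use of systemic antibacterial or antifungal agents in the past 3 months", and nasal steroids and acute hospitalization have the same window. Chlorhexidine appears in that list only as an allergy history: "History of an allergic reaction to chlorhexidine or mupirocin".

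Section 7.2 has participants apply the chlorhexidine cleanser "topically 3 times within 5 days before the Week 9 visit". Section 8.1 directs it to all skin below the neck. Three of the five sampled sites are skin.

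The only limit on antiseptics is in Section 8.1, where participants are told to "refrain from using any antibacterial/antiseptic products for 48 hours before visits". At Day 0 this counselling is listed after the specimens are taken. The step that confirms abstention first appears at Week 4. Section 5.5 permits all medications during the study and removes post-antibiotic data from the primary analysis, without mentioning antiseptics.

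On access to the agent, Section 2.1 says of chlorhexidine: "It is available as a topical solution ranging in concentration from 0.5% to 4% without a prescription". On the source population, Section 5.1 draws on "patients with cultures positive for S. aureus in the last three years" and adds "we will recruit from students and employees of the University of Maryland Baltimore and the VA Maryland HCS".

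**The concern.** The protocol guards the nasal baseline against recent use of the nasal agent's class for 3 months. It sets no comparable guard for the skin baseline against the skin agent's class and gives no reason for the difference. At Weeks 4 and 8 the 48-hour abstention partly fills that gap. At Day 0 nothing does.

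This matters because the study has one arm and Section 11.3 relies on each participant as his or her own control. No concurrent comparator within this protocol can correct a shifted baseline. A participant who washed with an antiseptic shortly before Day 0 would show a skin flora already moved in the direction of treatment, and so a smaller measured change. The Day 0 cultures also decide who stays in the study (Sections 5.2 and 5.4), so a recent wash could affect whether a skin site grows *S. aureus*. One positive site of the five is enough for eligibility, which limits that second effect.

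**Working it through.** **Step 1. Restrictions on antiseptic use at each baseline set.**

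- Exclusion window for prior antiseptic use (Section 5.3): none, against 3 months for nasal ointment and systemic antibacterials.
- Day 0 (Section 8.1): no prior instruction listed and no confirmation listed.
- Week 4 (Section 8.1): instruction given at Day 0; 48-hour abstention confirmed at the visit.
- Week 8 (Section 8.1): instruction given at Week 4; 48-hour abstention confirmed at the visit.

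The unprotected set is therefore Day 0, one of three.

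**Step 2. Age of any pre-enrollment use at the later sets.** At the nominal visit times it is at least 4 weeks old by Week 4 and 8 weeks old by Week 8. The timing guidelines in Section 8.1 allow baseline sets as close as 2 weeks apart, so the minimum is 2 and 4 weeks. Use between visits, up to 48 hours before a visit, is not restricted.

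**Step 3. Size, on assumed inputs.** The protocol gives no figure for prior antiseptic use or for how long its effect lasts. Its only related figure is the final sample size in Section 11.3, which reproduces as 250 × 1/5 − 10 = 40. The attenuation below does not depend on it.

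Let *f* be the share of participants with recent use, *r* the share of a full-course effect still present in an affected specimen, and *D* the true mean change on some scalar skin-site summary. Assume that post-treatment values are unaffected by the earlier use.

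- If *k* of the three baseline sets are affected and the sets are averaged, an exposed participant's baseline is shifted by *r* × *D* × *k*/3.
- The mean measured change is then *D* × (1 − *f* × *r* × *k*/3), so the relative attenuation is *f* × *r* × *k*/3.

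With only Day 0 affected (*k* = 1):

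- *f* = 10%, *r* = 50%: 0.10 × 0.50 / 3 = 1.7%.
- *f* = 30%, *r* = 50%: 0.30 × 0.50 / 3 = 5.0%.
- Wider range, *f* = 5%, *r* = 25%: 0.05 × 0.25 / 3 = 0.4%.
- Wider range, *f* = 20%, *r* = 100%: 0.20 × 1.00 / 3 = 6.7%.

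If Week 8 alone were the reference (*k* = 0), attenuation from an effect confined to Day 0 would be zero. If Day 0 alone were the reference, the divisor of 3 drops out and the first two values become 5% and 15%.

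Among 40 completers, *f* = 10% to 30% corresponds to 4 to 12 recent users.

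**The case against.** The strongest reply is that this is an eligibility preference. No sentence in the protocol says that prior antiseptic users are excluded, so nothing is literally contradicted. A prescription nasal antibiotic and a non-prescription skin antiseptic need not share a washout, and the Gram-negative concern in Section 2.2 is built mainly on intranasal mupirocin. This stands against any claim that a 3-month chlorhexidine window is required. It does not explain why the 48-hour rule, which the protocol itself considers worth confirming at every later weekly and monthly visit through Week 16, is absent at Day 0.

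Several safeguards also stand:

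- Anyone given a combined mupirocin and chlorhexidine course within 3 months is already removed by the nasal-ointment criterion.
- The hospitalization exclusion removes another likely route of exposure.
- Participants must be culture-positive at enrollment, which selects against those recently and successfully decolonized.
- The Day 0 history covers current and recent medications and may capture some use. A non-prescription wash is not named there, however, and the procedures and case report forms that Section 8.1 cites are not shown.

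Three stronger readings are tempting, and the documents do not support them:

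- A reader might take the follow-up at Weeks 9 to 16 and Month 12 as the protocol's admission that chlorhexidine persists on skin well beyond 48 hours. That schedule follows the combined regimen at all five sites, and Section 11.2 uses the follow-up to time re-colonization. It says nothing about persistence.
- A reader might apply the attenuation to the whole baseline and arrive at 5% to 15%. That treats Weeks 4 and 8 as if they were as exposed as Day 0.
- A reader might call the skin baseline the study's endpoint. Section 4.1 refers to the baseline microbiome as a whole, and nose and throat have their own baselines.

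**Conclusion.** The gap is real but small. Section 5.3 has no criterion for prior antiseptic wash, and the 48-hour abstention neither applies nor is checked at Day 0. Day 0 skin specimens can therefore reflect recent antiseptic use, probably biasing the skin-site change towards zero. Weeks 4 and 8 are largely protected.

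The size cannot be determined from the documents. The illustrative 1.7% to 5% rests on an assumed 10% to 30% of recent users, an assumed half of the full effect, contamination confined to Day 0, and simple averaging of the three sets. It also treats the change as a single additive quantity, which is a simplification for community composition data. This is a low-cost improvement to the baseline and does not undermine the study. Whether skin needs an exclusion window, and of what length, is for the sponsor to justify.

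**What to change.** Reconcile Sections 5.3, 5.5 and 8.1 on antiseptic use, as follows.

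1. Give the 48-hour abstention instruction when the enrollment visit is scheduled (Section 5.1 already provides for that contact), and add the confirmation step to the Day 0 list. Section 12 requires consent before any study procedure, so the IRB should agree to the wording of a pre-visit request.
2. At Day 0, ask about and record recent use of chlorhexidine or other antiseptic wash, with the approximate date of last use.
3. Plan a skin-site sensitivity analysis that omits either reported recent users or their Day 0 specimens. The second option keeps the participant and uses the Week 4 and Week 8 sets as baseline.
4. Either add a prior-antiseptic-use criterion to Section 5.3 with a window that the sponsor justifies, or state why the skin sites need none.

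The cost is one interview question, one confirmation step and one extra analysis. Recall of non-prescription washes will be imperfect, and a new criterion might shrink the eligible pool somewhat in a study that enrolls 250 to finish with 40. For participants already enrolled, the sensitivity analysis is limited to those whose exposure was recorded.
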